2.2 Objectives

2.2.1 Primary objective

The primary objective of this study is:

To evaluate the safety and tolerability of multiple doses of VIR-2218 in subjects with HBeAg-negative and HBeAg-positive chronic HBV infection without cirrhosis on NrtI therapy.

2.2.2 Secondary objectives

The secondary objectives of this study are:

- To characterize the PK of VIR-2218 in subjects with chronic HBV infection without cirrhosis on NrtI therapy.
- To assess the antiviral activity of VIR-2218 in subjects with chronic HBV infection without cirrhosis on NrtI therapy.

CCI [REDACTED]

[REDACTED]

[REDACTED]

2.3 Endpoints

2.3.1 Primary endpoints

- Incidence of treatment-emergent adverse events (TEAEs).
- Clinical assessments including but not limited to laboratory test results.

2.3.2 Secondary endpoints

- PK parameters of VIR-2218 and possible metabolites (may include, but not limited to, maximum plasma concentration, time to reach maximum concentration, area under the concentration versus time curve [to last measurable timepoint and to infinity], percent of area extrapolated, apparent terminal elimination half-life, clearance, and volume of distribution).
- Maximum reduction of serum HBsAg from Day 1 until 12 weeks post last dose.
- Number of subjects with serum HBsAg loss at any timepoint.
- Number of subjects with sustained serum HBsAg loss for greater than or equal to 6 months.
- Number of subjects with anti-HBs seroconversion at any timepoint.
- For HBeAg-positive subjects (Part Two only): number of subjects with HBeAg loss and/or anti-HBe seroconversion at any timepoint.

CCI [REDACTED]

[REDACTED]

[REDACTED]

[REDACTED]

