## PROTOCOL SYNOPSIS

A Phase 2 Randomized, Placebo-Controlled Study in Mainland China to Evaluate the Safety, Tolerability, Pharmacokinetics and Antiviral Activity of VIR-2218	
Planned to be conducted at multiple clinical investigative sites in mainland China.	
Phase 2	
Up to 30 subjects	
Up to 30 adult subjects with HBeAg-negative or HBeAg-positive chronic hepatitis B virus (HBV) without cirrhosis on nucleos(t)ide reverse transcriptase inhibitor (NrtI) therapy.	
Adult subjects with chronic HBV infection without cirrhosis on NrtI therapy.	
Inclusive of screening to post-dose follow-up, the estimated total time on study for each subject is up to 20 weeks: screening period (4 weeks), dosing period (4 weeks) and post-dose follow-up period (12 weeks).	
Additional HBsAg monitoring is required for subjects with a $\geq 1$ $\log_{10}$ change from baseline (Day 1 predose level) decrease in HBsAg achieved by the Week 16 visit. Subjects will be followed until the HBsAg level returns to $> 90\%$ of the Day 1 predose level or Week 48, whichever comes earlier. Additional HBsAg monitoring may be discontinued at the Sponsor's discretion based on emerging data.	
Post-dose follow-up period:	
All subjects will be followed until Week 16.	
Extended follow-up period:	
Extended follow-up visits will occur every 4 weeks starting at Week 20 and up to Week 48.	

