### **Extended follow-up period:**

Subjects who require additional HBsAg monitoring will return to the clinical investigational site for in-person assessments. Extended follow-up visits will occur every 4 weeks starting at Week 20, and subjects will be followed until the HBsAg level returns to > 90% of the Day 1 predose level or Week 48, whichever comes earlier. Additional HBsAg monitoring may be discontinued at the Sponsor's discretion based on emerging data.

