Blood sample for HBsAg	X	X	X	X	X	X	X	X	X	X	X	X	X	X	X	X
Blood sample for anti-HBs	X										X		X		X	Xs
Blood sample for HBeAg qualitative	X															
Blood sample for HBeAg quantitative for Part Two only t		X					X				X	X	X		X	Xs
Blood sample for anti-HBe for Part Two only	X										X		X		X	Xs
Blood sample for HBV DNA quantitation u	X	X					X				X	X	X	X	X	Xs

Study Stage	Screening		Dosing Period					Post-dose Follow-up Period b				b	Extended Follow-up Period °			
Study Visit Week				W1	W2	W3	W4ª	W5	W6	W7	W8	W12	W16/ET	W20	W24	
Study Visit Day	D-28 to -1	D1ª	D2	D8	D15	D22	D29a	D36	D43	D50	D57	D85	D113	D141	D169	Q28D
±Visit Window				±2	±2	±2	±2	±2	±2	±2	±2	±7	±7/ET	±7	±7	±7

Review/record AEs x	X	
Concomitant Medications	X	
NrtI medication adherence	X	

AE = adverse event; ECG = electrocardiogram; ET = early termination; CCI surface antigen; HBV = Hepatitis B Virus; NrtI = nucleoside/nucleotide; PK = pharmacokinetics

HBeAg = hepatitis e-antigen; HBsAg = hepatitis B

Note: When scheduled at the same timepoints, the assessments of vital signs and 12-lead ECGs must be performed before blood sample collections.

- a Assessments performed predose unless otherwise specified.
- b If a subject withdraws prematurely from the study prior to their Week 16 visit, ET assessments should be performed.
- Additional HBsAg monitoring is required for subjects with  $a \ge 1 \log_{10}$  change from baseline (Day 1 predose level) decrease in HBsAg achieved by the Week 16 visit. Extended follow-up visits will occur every 4 weeks starting at Week 20, and subjects will be followed until the HBsAg level returns to > 90% of the Day 1 predose level or Week 48, whichever comes earlier. Additional HBsAg monitoring may be discontinued at the Sponsor's discretion based on emerging data.
- d A complete medical history will be taken at screening including HBV genotype if available. Any changes should be updated prior to dosing.
- e Evaluation of inclusion and exclusion criteria related to pregnancy testing, urine drug screen, medical history and concomitant medications prior to dosing.
- See Section 7.2.1 for assessments to be performed during a full physical examination.
- g Subjects' alcohol intake will be recorded while on study.

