2. PROJECT OVERVIEW

2.1 Study Design

This is a phase 2 randomized, double-blind, placebo-controlled study of VIR-2218 administered subcutaneously to adult subjects with chronic Hepatitis B Virus (HBV) infection without cirrhosis on nucleos(t)ide reverse transcriptase inhibitor (NrtI) therapy. The study is designed to evaluate the safety, tolerability, PK and antiviral activity of VIR-2218.

This study will be conducted in close collaboration with an ongoing phase 1/2 regional study being conducted in multiple sites in the Asia-Pacific region.

[figure not shown]
This study will include two Parts:

- Part One: adult subjects with Hepatitis B e-Antigen (HBeAg)-negative chronic HBV infection without cirrhosis on NrtI therapy for \geq 6 months and HBV DNA < 90 IU/mL at screening (by central laboratory)
- Part Two: adult subjects with HBeAg-positive chronic HBV infection without cirrhosis on NrtI therapy for \geq 6 months and HBV DNA < 90 IU/mL at screening (by central laboratory)

Each cohort in Part One/Two will be composed of 5 subjects randomized 4:1 to VIR-2218 or placebo, respectively. There are two planned cohorts (50 mg dose-level and 100 mg dose-level) and 1 optional cohort (\leq 200 mg dose-level) for each of Part One and Part Two of the study. Enrollment of the Part One/Two optional cohorts will be according to the same randomization scheme and eligibility criteria as the Part One/Two planned cohorts. The optional cohorts may be initiated after Safety Review Committee (SRC) review of a minimum of 6 weeks of available safety and antiviral activity data from the 200 mg cohorts of the VIR-2218-1001 regional study.

The estimated total duration for each subject is up to 52 weeks, including screening period (4 weeks), dosing period (4 weeks), post-second dose follow-up period (12 weeks) and extended follow-up period (up to 48 weeks) (Figure 1). Additional HBsAg monitoring is required for subjects with a ≥ 1 \log_{10} change from baseline (Day 1 pre-dose level) decrease in HBsAg achieved by the Week 16 visit. Extended follow-up visits will occur every 4 weeks starting at Week 20, and subjects will be followed until the HBsAg level returns to $> 90\%$ of the Day 1 pre-dose level or Week 48, whichever comes earlier. Additional HBsAg monitoring may be discontinued at the Sponsor's discretion based on emerging data.

Figure 1. Study Design for Cohorts

Screening period

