Subjects who require additional HBsAg monitoring will return to the clinical investigational site for in-person assessments. Extended follow-up visits will occur every 4 weeks starting at Week 20, and subjects will be followed until the HBsAg level returns to $> 90\%$ of the Day 1 pre-dose level or Week 48, whichever comes earlier. Additional HBsAg monitoring may be discontinued at the Sponsor's discretion based on emerging data.

Discontinuations

Subjects who discontinue prematurely will be followed for safety, and under certain circumstances, subjects who discontinue study drug (as described in Protocol Amendment 2 section 4.3) may be replaced. If a subject discontinues from the study post-dose but before completion of the Week 16 visit, an early termination visit should be performed.

Replacement of Subjects

Replacement subjects may be enrolled to ensure that the minimum data requirements for SRC decisions and study progression are met, as described in Protocol Amendment 2 section 4.5. Subjects who do not receive the full planned dose, do not receive a second dose, discontinue due to an Adverse event (AE) that does not meet study progression and dose suspension/stopping rules (Protocol Amendment 2 section 4.6), or who withdraw from the study, may be replaced with confirmation by the SRC. Subjects who are discontinued from treatment for reasons other than experiencing an AE may be replaced following discussion between the Sponsor and investigator.

The replacement subject will be assigned a unique study identification number and will receive the same study drug assignment and dose level as the subject who is being replaced and in the same blinded fashion.

Safety Review Committee

An SRC will perform ongoing reviews of safety, tolerability, and available study data collected throughout the study with the primary purpose of protecting the safety of subjects participating in this clinical study. The SRC will be governed by an SRC Charter that will be finalized prior to screening the first subject.

The SRC will undertake safety data review prior to initiation of dosing the optional cohorts of the study in accordance with the SRC Charter. In addition, ad hoc SRC meetings may take place as needed, e.g., for a significant safety event such as a subject or cohort stopping criterion being reached (Protocol Amendment 2 section 4.6).

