13.1 Definition of variables

- Maximum reduction of serum HBsAg from Day 1 until Week 16.
 - Serum \log_{10} HBsAg levels by timepoint
 - Serum \log_{10} HBsAg Nadir level per subject
- Number of subjects with serum HBsAg loss.
- Number of subjects with sustained serum HBsAg loss for ≥ 6 months.
- Number of subjects with anti-HBs seroconversion.
- For HBeAg-positive subjects (Part Two only): number of subjects with HBeAg loss and/or anti-HBe seroconversion.

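### The Part Two count of HBeAg loss and/or anti-HBe seroconversion has no common window: HBsAg responders can be observed up to Week 48, all others only to Week 16, so the descriptive counts are not comparable across columns.

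*SAP*

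**What the plan says.** SAP 2.3.2 and Protocol 3.2 define the Part Two endpoint as the "number of subjects with HBeAg loss and/or anti-HBe seroconversion at any timepoint". SAP 13.1 restates it as the "number of subjects with HBeAg loss and/or anti-HBe seroconversion", again with no closing week. The same list does close another endpoint: "Maximum reduction of serum HBsAg from Day 1 until Week 16".

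Follow-up is not the same for everyone. The Protocol Synopsis says "All subjects will be followed until Week 16". Beyond that, SAP 2.1 requires further monitoring only for subjects with at least a 1 log10 "change from baseline (Day 1 pre-dose level) decrease in HBsAg achieved by the Week 16 visit". For them, Protocol Appendix 2 (footnote c) says "Extended follow-up visits will occur every 4 weeks starting at Week 20". They continue until HBsAg is back above 90% of the Day 1 level "or Week 48, whichever comes earlier", and the sponsor may stop the monitoring sooner.

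Protocol Appendix 2 schedules quantitative HBeAg in Part Two on Day 1 and at Weeks 4, 8, 12 and 16, then at Weeks 24, 36 and 48 in extended follow-up. Anti-HBe is drawn at screening and Weeks 8 and 16, then at Weeks 24, 36 and 48. Neither is drawn at Week 20.

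SAP 3.2 defines HBeAg loss as a quantitative result under 0.14 IU/mL on at least two consecutive measurements. Seroconversion is that loss plus anti-HBe positivity, so the and/or composite reduces to HBeAg loss. SAP 3.6 and 13 tabulate results by cohort, with the placebo column beside the doses.

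**The concern.** How long a subject is observed for this endpoint depends on an HBsAg response after randomization, which the drug is meant to cause. Protocol 1.2.4 reports HBsAg reductions at 50 mg and 100 mg in the regional study. Protocol 1.2.2 says that NrtIs do not act directly on HBsAg production. Placebo subjects, who stay on NrtI alone, will therefore probably almost all leave at Week 16, while some active subjects stay longer and have more chances to show a confirmed HBeAg loss.

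A higher count in an active column could then reflect longer observation and not an effect on HBeAg. The same applies between two active cohorts with different numbers of HBsAg responders. In a table this small, one late event could be the whole apparent difference.

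**Working it through.** **The plan's own figures.** There is no power calculation to reproduce. Durations: 4 + 4 + 12 = 20 weeks from screening to Week 16 (Protocol Synopsis), and 4 + 48 = 52 weeks for a subject followed to Week 48 (Protocol 4.1, SAP 2.1). The components listed for the 52 weeks add to 4 + 4 + 12 + 48 = 68, so the last item has to mean until Week 48. Subjects: 2 parts × 3 cohorts × 5 = 30. Part Two has 8 active and 2 placebo subjects in the planned cohorts, or 12 and 3 with the optional cohort.

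**Opportunities to meet the definition** (Protocol Appendix 2 and the two-consecutive rule in SAP 3.2; n post-baseline samples give n − 1 consecutive pairs):

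| | Leaves at Week 16 | Followed to Week 48 |
|---|---|---|
| HBeAg samples | 4 (W4, 8, 12, 16) | 7 (adds W24, 36, 48) |
| Consecutive HBeAg pairs | 3 | 6 |
| Latest first negative that can be confirmed | Week 12 | Week 36 |
| Anti-HBe samples (pairs) | 2 (1) | 5 (4) |

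A subject whose extension ends at Week 24 has a latest confirmable first negative at Week 16. One whose extension ends at Week 20 gains nothing for HBeAg. The anti-HBe pairs matter only for a separate seroconversion row.

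**Size with no drug effect on HBeAg.** Assume permanent loss at a constant rate h per patient-year, equal in all arms. The chance of a countable loss is P(w) = 1 − exp(−h × w/52), where w is the latest confirmable week. Assume that a share q of active subjects is extended and no placebo subject is. The active percentage is (1 − q) × P(12) + q × P(w), with w = 16 (extension to Week 24) or w = 36 (extension to Week 48). The documents give neither h nor q.

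For h = 0.10 and q = 0.5:
- P(12) = 1 − exp(−0.10 × 12/52) = 2.28%; P(16) = 3.03%; P(36) = 6.69%.
- Extension to Week 24: (2.28 + 3.03)/2 = 2.66%; ratio 2.66/2.28 = 1.16.
- Extension to Week 48: (2.28 + 6.69)/2 = 4.49%; ratio 4.49/2.28 = 1.97.

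| h per 100 patient-years | P(12) | P(36) | Ratio, q = 0.5, to W24 | Ratio, q = 0.5, to W48 | Extra events in 12 active, q = 0.5, to W48 |
|---|---|---|---|---|---|
| 5 | 1.15% | 3.40% | 1.17 | 1.98 | 0.14 |
| 10 | 2.28% | 6.69% | 1.16 | 1.97 | 0.26 |
| 20 | 4.51% | 12.93% | 1.16 | 1.93 | 0.51 |

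At h = 0.10, 8 active subjects give 8 × (4.49% − 2.28%) = 0.18 extra events.

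Other shares extended to Week 48, at h = 0.10: the ratio is 1.48 for q = 0.25, 2.45 for q = 0.75 and 2.93 for q = 1.

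The excess reaches one event only at the extremes. With all 12 active subjects followed to Week 48 it is 12 × (12.93% − 4.51%) = 1.01 at 20 per 100 patient-years. At an annual risk of 40% it is 1.1 with half extended and 2.2 with all.

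**After a common Week 16 window.** Every subject has 3 HBeAg pairs and a latest confirmable first negative at Week 12, so the expected ratio with no effect is 1.0.

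**The case against.** SAP 3.3 plans no hypothesis test and the analysis is descriptive. A reader might infer that a formal active-versus-placebo or dose comparison is biased, or that a type I error rate is inflated. The documents contain no such comparison. What is affected is how a table is read across its columns.

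A reader might also infer that every HBsAg responder is counted to Week 48. That is a ceiling: follow-up ends earlier on HBsAg rebound or by sponsor decision, and the ratio of about 2.0 needs half of active subjects to reach Week 48. Nor do the documents show that low-dose subjects lose most, since Protocol 1.2.4 reports reductions at both 50 mg and 100 mg without a gradient. No denominator is stated for this cumulative count. SAP 3.1 uses subjects with non-missing data, and keeping those who left at Week 16 in the denominator is my reading of it.

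Protocol 9.7 and SAP 13.2 already provide summaries by visit, with plots and listings. With at most 15 Part Two subjects, the timing of any event will be visible. Rows through Week 16 are like for like. They do not give a cumulative, confirmed Week 16 count, and with non-missing denominators the later rows contain only HBsAg responders.

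The absolute effect is also small. At 10 per 100 patient-years the chance of no placebo event is 95% with 2 placebo subjects and 93% with 3, so the placebo cell will most likely read zero with or without the change. All of this limits the size of the point. None of it supplies a common window.

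**Conclusion.** The point stands as one of definition and labelling. Observation for the Part Two HBeAg count depends on HBsAg response, no text in the protocol or SAP sets a common window, and the resulting direction favours groups with more HBsAg responders. The three-fold difference in the confirmable window (Week 12 against up to Week 36) comes from the schedule alone.

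The null ratios of about 1.2 to 2.0 rest on an assumed constant background rate, half of active subjects extended and no placebo subject extended. The expected excess is below one event in most scenarios. The table becomes misleading only if an HBeAg loss is confirmed after Week 16.

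The counts of HBsAg loss and anti-HBs seroconversion share the open window but are less exposed. Falling from the entry minimum of 150 IU/mL to 0.05 IU/mL needs log10(150/0.05) = 3.5 log10, which a subject without a 1 log10 fall by Week 16 is unlikely to reach. HBeAg loss has no such built-in link to the HBsAg trigger.

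**What to change.** In SAP 13.1 and 13.2, before database lock and unblinding:

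1. As the between-group summary, report the number of Part Two subjects with HBeAg loss, and with seroconversion, confirmed by two consecutive measurements on data through Week 16.
2. In a separate row, report all events whose confirming measurement falls after Week 16. Define the row by the date of confirmation, so that a first negative at Week 16 confirmed at Week 24 is included and no event falls between rows. Use the number of subjects in extended follow-up as the denominator, with a footnote that entry depended on HBsAg response.
3. Keep the any-timepoint count as a total, labelled as based on unequal follow-up.

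The cost is SAP wording and one or two table rows, with no new data or visits. The downside is that late-confirmed events leave the headline comparison, although they are still reported.

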2.4 Sample Size

No formal sample size calculation was conducted. Up to 30 subjects with chronic HBV infection are planned to complete the study.

2.5 Randomization

An Interactive Web Response System (IWRS) will be employed to manage subject randomization and treatment assignments.

For each of the planned 50 and 100 mg dose-level cohorts, 5 subjects will be randomized 4:1 to VIR-2218 or placebo administered 4 weeks apart on Day 1 and Week 4.

One optional cohort may be added to each study part (Part One and Part Two), wherein 5 subjects will be randomized 4:1 to VIR-2218 or placebo administered 4 weeks apart on Day 1 and Week 4 at a dose-level of up to 200 mg.

Blinding of study treatment will be managed by the clinical investigative site's pharmacy in accordance with the Pharmacy Manual. In the event of a medical emergency where breaking the blind is required to provide medical care to the subject, the investigator may obtain treatment assignment for that subject. IWRS should be used as the primary method of breaking the blind. If IWRS cannot be accessed, the investigator should contact the Sponsor medical monitor to break the blind. Treatment assignment should remain blinded unless that knowledge is necessary to guide subject emergency medical care. The investigator is requested to contact the Sponsor medical monitor promptly in case of any treatment unblinding.

Blinding of study treatment is critical to the integrity of this clinical study and therefore, if a subject's treatment assignment is disclosed to the investigator, the subject will have study treatment discontinued. All subjects will be followed until study completion unless consent to do so is specifically withdrawn by the subject.

The Sponsor or designee may independently unblind cases for expedited reporting of suspected unexpected serious adverse reactions (SUSARs) as required by regulators.

3. STATISTICAL CONSIDERATIONS

Data will be handled and processed per the sponsor's representative PPD Standard Operating Procedures (SOPs), which are written based on the principles of good clinical practice (GCP).

3.1 General Considerations

All data collected on the electronic case report form (eCRF) will be presented in the data listings and will be listed and sorted by treatment arm, subject number and visit, where applicable. All summaries will be presented by treatment arm.

When reporting descriptive statistics, the following rules will apply:

- **Continuous variables:** Descriptive statistics for observed data or log10-transformed observed values, where applicable, will include the number of non-missing values (n), arithmetic mean, standard deviation (SD), median, first quartile (Q1), third quartile (Q3), minimum and maximum values. The minimum and maximum are the smallest and largest arithmetic values, respectively, unless specified otherwise.

The Q1, Q3, minimum and maximum values will be displayed to the same decimal precision as the source data; the arithmetic mean and median values will be displayed to one more decimal than the source data; SD value will be displayed to two more decimal than the source data for the specific variable.

The appropriate precision for derived variables will be determined based on the precision of the data on which the derivations are based, and statistics will be presented in accordance with the abovementioned rules.

n will be an integer. If no subjects have data at a given time point, then only n=0 will be presented.

All data will be presented to a maximum of 3 decimal places.

- **Categorical variables:** Descriptive statistics will include counts and percentages per category. The denominator in all percentage calculations will be the number of subjects in the relevant analysis set with non-missing data, unless specifically stated otherwise. Percentages will be displayed to one decimal place.

Percentage change from baseline values will be calculated and displayed to 1 decimal place in the listings. In the summaries, the mean and median percentage change from baseline values will be presented to 2 decimal places, the minimum and maximum values will be presented to 1 decimal place and the SD value will be presented to 3 decimal places.

For categories where all subjects fulfill certain criteria, the percentage value will be displayed as 100. For categories where zero subjects fulfill certain criteria, there will be no percentage displayed. All other percentage displays will use 1 decimal place. Data listings will contain all reported and derived data.

Unless otherwise stated, the following methods will be applied:

- **Repeat/unscheduled assessments:** Only values collected at scheduled study visits/time points will be presented in summary tables. Repeat and unscheduled assessments will be included in the derivation of the baseline values and minimum/maximum values post baseline. If a repeat assessment was performed, the result from the original assessment will be presented as the result at the specific visit/time point. For screening visits, there are some repeated lab results because the original results may be errors. Then the repeated results will be presented as screening results for these cases. All collected data will be included in the data listings.

- **Assessment windows:** All assessments will be included in the data listings and no visit windows will be applied to exclude assessments that were performed outside of the protocol specified procedure windows.
- **Result display convention:** Results will be center aligned in all summary tables and listings. Subject identifiers visit and parameter labels may be left-aligned if required.
- **Date and time display conventions:** The following display conventions will be applied in all outputs where dates and/or times are displayed:
 - Date only: YYYY-MM-DD
 - Date and time: YYYY-MM-DD HH:MM

If only partial information is available, unknown components of the date or time will be presented as 'NK' (not known), i.e., '2016-NK-NK'. Times will be reported in military time.

